#### 4.3.1.1 Nivolumab Dosing

Patients in combination therapy cohorts will receive the nivolumab infusion first at a dose of 3 mg/kg as a 30-minute IV infusion, on Day 1 of each 14 or 21 day treatment cycle depending on

treatment cohort. If any Grade 3 or higher infusion reaction is observed during the proposed infusion rate of nivolumab 3 mg/kg over 30 minutes, the infusion rate will be extended to 60 minutes for all current and subsequent patients for the duration of this study.

There will be no dose escalations or reductions of nivolumab allowed. Patients may be dosed no less than 12 days from the previous dose. There are no premedications recommended for nivolumab on the first cycle. Refer to the Pharmacy Manual for nivolumab preparation instructions.

#### 4.3.1.2 Cabiralizumab Dosing

For patients in the combination therapy cohorts, the cabiralizumab infusion will be administered 30 minutes IV infusion, after the end of the nivolumab infusion and a 30- to 60-minute rest, on Day 1 of each 14 or 21 day treatment cycle depending on treatment cohort. For patients in the monotherapy cohorts, the cabiralizumab infusion can be initiated at any time as a 30-minute IV infusion on Day 1 of each 14-day treatment cycle.

Cabiralizumab dosing may be modified based on toxicities noted during the treatment period. If necessary, the dose will be adjusted ( [REDACTED] ) and Sections 4.3.2, 4.3.4, 4.3.5, and 4.3.10.

A research pharmacist (or other responsible personnel) will prepare the solution for administration. After calculating the number of vials, based on the patient's weight, the study drug product will be diluted with 0.9% Sodium Chloride Injection, USP. Prepared cabiralizumab should be administered within 6 hours after preparation (ambient temperature). The IV administration setup for cabiralizumab infusion must contain a 0.2 or 0.22 µm in-line filter or a 0.2 or 0.22 µm syringe filter. Cabiralizumab will be administered under medical supervision as a 30 minute (± 5 minutes) IV infusion via a peripheral vein or central venous catheter. No incompatibilities between cabiralizumab infusion and polyvinyl chloride (PVC), ethylene/propylene IV components, or glass bottles have been observed.

#### 4.3.2 Dose Delay for Cabiralizumab and Nivolumab

Administration of cabiralizumab and/or nivolumab in combination therapy should be delayed for the following:

- Any Grade 3 fatigue which does not resolve to Grade 1 or baseline before the next treatment visit
- Any drug-related laboratory abnormalities would not require a dose delay unless clinically indicated or specified in the protocol or abnormal laboratory management table (Appendix H). Please discuss with the Sponsor's Medical Monitor or designee as needed.

[REDACTED]

Patients who require a dose delay of cabiralizumab or cabiralizumab /nivolumab should be re-evaluated weekly or more frequently if clinically indicated and resume study drug dosing when re-treatment criteria are met.

If a patient experiences an infusion reaction to cabiralizumab, or nivolumab, or both study drugs, the infusion reaction should be treated following the infusion reaction treatment guidelines [REDACTED]

If the causality of the AE requiring a dose delay is confirmed to be due to one of the study drugs of the combination therapy, the non-offending drug may be continued per protocol taking into account the safety and clinical benefit to the patient.

#### 4.3.3 Criteria to Resume Treatment with Cabiralizumab and Nivolumab

Patients may resume treatment with cabiralizumab and/or nivolumab when the drug-related AE resolves [REDACTED]

[REDACTED] The Sponsor's Medical Monitor or designee can be contacted at any time if further clarification is needed.

#### 4.3.4 Dose Reduction with Cabiralizumab and Nivolumab

Dose reduction for cabiralizumab and nivolumab are not permitted.

#### 4.3.5 Dose Discontinuation Criteria for Cabiralizumab and Nivolumab

Discontinuation rules may be different for monotherapy and combination therapy and not all rules will apply to both arms of the study. [REDACTED]

Treatment of cabiralizumab in monotherapy or cabiralizumab in combination with nivolumab should be discontinued in the following cases unless otherwise specified:

- Any Grade 3 or higher uveitis *or* any Grade 2 drug-related uveitis, eye pain, or blurred vision that does not respond to topical therapy and does not improve to Grade 1 within the second re-treatment period *or* that requires systemic treatment
- Any Grade 3 or higher infusion-related reactions and hypersensitivity requiring discontinuation. Any re-initiation of therapy in this circumstance would require consultation with the Sponsor's Medical Monitor or designee.
- Any Grade 3 non-skin, drug-related AE lasting >7 days, including drug-related uveitis, pneumonitis, hypoxia, bronchospasm, and endocrinopathies with the following exceptions:
  - Grade 3 drug-related endocrinopathies adequately controlled with only physiologic hormone replacement do not require discontinuation
  - Grade 3 drug-related laboratory abnormalities do not require treatment

discontinuation except:

- Grade 3 drug-related thrombocytopenia >7 days or associated with Grade  $\geq 2$  bleeding requires discontinuation
- Any drug-related liver function test (LFT) abnormality that meets any one of the following criteria requires discontinuation:
  - ALT or AST >3x ULN **and** total bilirubin >2x ULN **or** INR > 1.5 xULN (in the absence of anticoagulation).
  - [REDACTED]
  - ALT or AST > 20x ULN (with or without concurrent liver metastases)
  - Total bilirubin >3x ULN (>5x ULN with concurrent liver metastases)
- Any Grade 4 drug-related AE or laboratory abnormality, except for the following events which do not require discontinuation:
  - Grade 4 neutropenia <7 days
  - Grade 4 lymphopenia or leukopenia <7 days
  - Isolated Grade 4 amylase or lipase abnormalities that are not associated with symptoms or clinical manifestations of pancreatitis. The Sponsor’s Medical Monitor or designee should be consulted for Grade 4 amylase or lipase abnormalities.
  - Isolated Grade 4 electrolyte imbalances/abnormalities that are not associated with clinical sequelae and are corrected with supplementation/appropriate management within 72 hours of their onset
  - Grade 4 drug-related endocrinopathy AEs, such as adrenal insufficiency, adrenocorticotrophic hormone (ACTH) deficiency, hyper- or hypothyroidism, or glucose intolerance, which resolve or are adequately controlled with physiologic hormone replacement (corticosteroids, thyroid hormones) or glucose-controlling agents, respectively, may not require discontinuation after discussion with and approval from the Sponsor’s Medical Monitor or designee.
  - Grade 4 CK up to 20 xULN (in the absence of clinical sequelae)
- Any event that leads to delay in dosing lasting > 6 weeks from the previous dose requires discontinuation, with the following exceptions:
  - Dosing delays to manage drug-related adverse events are allowed. Prior to re-initiating treatment in a patient with a dosing delay lasting > 6 weeks from the previous dose, the Sponsor’s Medical Monitor or designee must be consulted. Tumor assessments should continue as per-protocol even if dosing is delayed. Periodic study visits to assess safety and laboratory studies should also continue per protocol, or more frequently if clinically indicated during such dosing delays or per the Investigator’s discretion.

- Dosing delays lasting > 6 weeks from the previous dose that occur for non-drug-related reasons may be allowed if approved by the Sponsor’s Medical Monitor or designee. Prior to re-initiating treatment in a patient with a dosing delay lasting > 6 weeks, the Sponsor’s Medical Monitor must be consulted. Tumor assessments should continue per protocol every 8 weeks ( $\pm 7$  days) even if dosing is delayed. Periodic study visits to assess safety and laboratory studies should also continue per-protocol or more frequently if clinically indicated during such dosing delays or per the Investigator’s discretion.
- Any AE, laboratory abnormality, or intercurrent illness which, in the opinion of the Investigator, presents a substantial clinical risk to the patient with continued cabiralizumab and/or nivolumab dosing
- Any drug-related Grade 3 or higher neurological toxicity
- Any Grade 3 or higher periorbital edema and persistent Grade 2 periorbital edema requiring 2 missed doses unless approved by Sponsor’s Medical Monitor
- Any Grade 3 or higher drug-related diarrhea or colitis, which does not resolve to Grade 1 or baseline within 28 days.
- Any Grade 4 skin toxicity
- Any Grade 4 renal toxicity
- Any drug-related Grade 3 or higher pulmonary toxicity

If the causality of the adverse event requiring discontinuation is confirmed to be due to one of the study drugs in the combination therapy, the other drug may be continued per protocol schedule under the following scenarios:

- Timely resolution of the adverse event based on the treatment modification table
- Clinical benefit is shown by the patient based on Investigator assessment

#### **4.3.6 Infusion Delays and Missed Doses with Cabiralizumab and Nivolumab**

In case an infusion cannot be administered at a scheduled visit, it must be administered as soon as possible. If the delay is between 1 and 7 days, the procedures at the original scheduled visit should be performed. If the delay is more than 7 days, the infusion at the original scheduled visit will be considered a missed dose and the procedures at the next visit should be performed. If the delay is longer than 7 days, subsequent visits will follow a 2-week (or 3-week in Phase 1a 3-week dosing regimen cohort) dosing interval. If the delay is less than 7 days, the original dosing schedule should be followed. The time between two treatment cycles should be no less than 12 days.

Patients may miss up to up to 6 weeks between doses and may resume the study drug if the event returns to baseline or  $\leq$  Grade 1 within 6 weeks of treatment interruption. Omission of additional dosing longer than 6 weeks for AEs will necessitate the patient’s discontinuation from the study unless allowed by the Sponsor’s Medical Monitor or designee. Patients may miss doses in the

course of participation in the study, including missed doses for scheduled vacations or other personal reasons as needed, but not more than 6 weeks unless approved by the Sponsor's Medical Monitor or designee.

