## 4.3 Study Drug Dosing and Dose Modification

### 4.3.1 Dosing

For patients in the monotherapy cohorts, cabiralizumab infusion may be administered as a 30-minute IV infusion on Day 1 of each 14-day treatment cycle. For the combination therapy, nivolumab should always be administered first as a 30-minute IV infusion, with a 30- to 60-minute rest, followed by a 30-minute infusion of cabiralizumab (patients in 3-week dosing regimen cohort will receive study drugs on Day 1 of each 21-day treatment cycle). If any Grade 3 or higher infusion reaction is observed during the proposed infusion rate of nivolumab 3 mg/kg over 30 minutes, the infusion rate will be extended to 60 minutes for all current and subsequent patients for the duration of this study. Patients may be dosed no less than 12 days from the previous dose.

For Cohort 1aM2, 6 mg/kg cabiralizumab monotherapy, and dose escalation Cohorts 1aC2 and 1aC3, cabiralizumab and nivolumab combination therapy, the dose interval between the first and second patients in each cohort should be at least 24 hours for safety monitoring.

Dosing calculations should be based on the body weight assessed at Cycle 1 Day 1 prior to the first dose of study drug administration. It is not necessary to recalculate subsequent doses if the patient's weight is within 10% of the weight used to calculate the previous dose. All doses should be rounded to the nearest milligram.

Patients should be carefully monitored for infusion reactions during study drug administration. If an acute infusion reaction is noted, patients should be managed according to the guidelines in Section 4.3.10 [REDACTED]

Doses of study drugs may be interrupted, delayed, or discontinued depending on how the patient tolerates the treatment.

All vials are for single use only. Further instructions on study drug preparation and administration are provided in the Pharmacy Manual.

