#### 7.7.2 **PK Parameters**

The PK evaluable population will be used for all summaries of the PK parameters. Summary statistics will be tabulated for each PK parameter by individual or combined cohort with different dose and regimen. Geometric means and coefficients of variation will be presented for Cmax, AUC(0-T), AUC(TAU), Cmin, Ctrough, CL, Vss, MRT and AIs. Medians and ranges (minimum and maximum) will be presented for Tmax. Means and standard deviations will be presented for other PK parameters (i.e., t1/2).

Pharmacokinetic parameters of cabiralizumab will be derived from the serum concentration versus time profiles for the intensively sampled Cycle 1, Day 1 and Cycle 8, Day 1 dose administration in both Phase 1a and Phase 1b of the study. Individual PK parameter values will be derived by non-compartmental methods by a validated PK analysis program using actual times.

Parameter	Units	Definition
Cmax	µg/mL	Maximum observed serum concentration
Tmax	h	Time of maximum observed serum concentration
AUC(0-T)	μg.d/mL	Area under the serum concentration-time curve from time zero to time of last quantifiable concentration
AUC(TAU)	µg.d/mL	Area under the serum concentration-time curve in one dosing interval
Cmin	µg/mL	Minimum observed serum concentration during a dosing interval (excludes pre-dose concentration before the first dose)
Ctrough	µg/mL	Concentration associated with the sample at the end of each dose interval.
CL	L/d	Total body clearance calculated Dose divided by AUC(TAU) for Cycle 8, Day 1
AI_AUC	-	AUC accumulation index; ratio of AUC(TAU) for Cycle 8, Day 1 to AUC(TAU) after the first dose
AI_Cmax	-	Cmax accumulation index; ratio of Cmax from any cycles to Cmax after the first dose
AI_Cmin	-	Cmin accumulation index; ratio of Cmin for Cycle 8, Day 1 to Cmin after the first dose
AI_Ctrough	-	Ctough accumulation index; ratio of Ctrough from any cycles to Ctrough after the first dose
pAUCe	%	Percent of AUC extrapolated from the last quantifiable concentration to infinity (Cycle 1, Day 1 only)
λz	d-1	Slope of terminal log-linear elimination phase
Adj R 	-	Adjusted R  of terminal elimination phase
Lz_Start	d	The time point starting the log-linear elimination phase defining the terminal half-life
Lz_End	d	The time point ending the log-linear elimination phase defining the terminal half-life

Parameter	Units	Definition			
Lz_N	-	Number of time points in the log-linear elimination phase defining the terminal half-life			

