### 7.7.4.2 PK Parameter Evaluation

For cabiralizumab, PK parameters including Cmax, AUC, Cmin, Ctrough, CL, Vss, and MRT will be estimated. The cabiralizumab accumulation ratio for Cmax, Cmin, and Ctrough, and AUC will be estimated for different cycles, as data permit. For nivolumab, Ctrough will be reported and accumulation will be evaluated for different cycles, as data permit.

Dose-proportionality will be assessed based on available cabiralizumab PK parameters if applicable.

Only data points that describe the terminal elimination log-linear decline will be used in the regression equation for calculation of  $\lambda_z$ .  $C_{max}$  and any data point in the distribution phase will not be included in the calculation of  $\lambda_z$ . A minimum of 3 points will be used for determination of the terminal elimination phase rate constant. A value of adjusted  $r^2 > 0.80$  will be considered acceptable for the calculation of the terminal elimination phase rate constant. If adjusted  $r^2$  falls below 0.80, or the above conditions are not met, then the terminal elimination phase rate constant and the associated values of t1/2, AUC(INF), CL and Vss will be flagged. If pAUCe is more than 20%, then AUC(INF) and CL will be flagged. Flagged values will not be included in the calculation of descriptive statistics.

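### Cycle 8 accumulation indices and clearance carry no dosing-history requirement, so doses missed or delayed shortly before Cycle 8 distort them; protocol 4.3.6 also conflicts with its own 12-day minimum

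*Protocol*

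**What the plan says.** **Visit numbering.** Protocol 4.3.6 distinguishes short from long delays. For short ones: "If the delay is between 1 and 7 days, the procedures at the original scheduled visit should be performed". For a delay beyond 7 days, the infusion "will be considered a missed dose and the procedures at the next visit should be performed". Up to 6 weeks between doses is allowed, or more with the Medical Monitor's agreement. Protocol 4.3.2 and 4.3.5 also let one drug continue while the other is held, so cycles can advance without cabiralizumab.

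**PK parameters.** SAP 7.7.2 defines CL as dose over AUC(TAU) at Cycle 8 Day 1 and Vss as CL times MRT. AI_AUC is the "AUC accumulation index; ratio of AUC(TAU) for Cycle 8, Day 1 to AUC(TAU) after the first dose", and AI_Cmin is built the same way. AI_Cmax and AI_Ctrough may come from any cycle. Ctrough is the "Concentration associated with the sample at the end of each dose interval".

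**Safeguards.** SAP 7.7.4.2 flags values on the quality of the terminal-phase fit and on pAUCe above 20%, and adds: "Flagged values will not be included in the calculation of descriptive statistics". The PK Evaluable Population (SAP 7.2) has no criterion on doses received. SAP 7.7.4.3 lets a profile be excluded after review but names no trigger.

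**Dosing interval.** Protocol 4.3.6 also says: "If the delay is less than 7 days, the original dosing schedule should be followed". Protocol 4.3.1 says: "Patients may be dosed no less than 12 days from the previous dose", and 4.3.6 repeats the 12-day minimum.

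**The concern.** Dose over AUC(TAU) equals clearance only at steady state, and an accumulation index read at Cycle 8 is interpretable only if the intended doses were given up to then. The plan treats the nominal cycle number as evidence of both. Actual sampling times correct the time axis of the profile, but they cannot restore a dose that was not given.

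CL and the accumulation ratio are secondary PK endpoints in both phases (SAP 4.2). PK may inform the recommended dose and alternative regimens (protocol 3.1.2.1). SAP 7.6.8 summarises troughs by post-baseline ADA status to explore effects on clearance. A low trough that only reflects a long gap could be read there as an immunogenicity effect.

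The dosing text has its own problem. In the 14-day cohorts, returning to the original calendar after some short delays breaks the stated minimum interval.

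**Working it through.** The documents give no PK value to reproduce. The only half-life figure is in protocol 6.5, which equates 5 half-lives with 90 days: 90/5 = 18 days, stated for the product and not for cabiralizumab specifically. I treat half-life as an assumption, 8 to 25 days, and use a linear one-compartment model with dosing interval τ = 14 days.

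**Formulas.** Let r = exp(−ln2 × 14 / t½). AUC(TAU) at Cycle 8 relative to the first dose is S = Σ r^(8−j) over the doses j actually given. Then AI_AUC = S, and apparent CL / true CL = [1/(1−r)] / S. With all eight doses given, S = (1−r⁸)/(1−r); missing Cycle 7 subtracts r. AI_Cmin falls in the same proportion when the minimum lies at the end of the Cycle 8 interval. For a first-dose profile followed to day 14, pAUCe = r.

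| t½ (d) | r = pAUCe | AI_AUC on time | AI_AUC, Cycle 7 missed | change | CL ratio on time | CL ratio, Cycle 7 missed |
|---|---|---|---|---|---|---|
| 8 | 0.297 | 1.42 | 1.13 | −21% | 1.00 | 1.26 |
| 14 | 0.500 | 1.99 | 1.49 | −25% | 1.00 | 1.34 |
| 18 | 0.583 | 2.37 | 1.78 | −25% | 1.01 | 1.35 |
| 25 | 0.678 | 2.97 | 2.29 | −23% | 1.05 | 1.36 |

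**Timing of the miss (t½ 18 d).** CL ratio for one missed dose:
- Cycle 2: 1.03
- Cycle 4: 1.07
- Cycle 5: 1.11
- Cycle 6: 1.18
- Cycle 7: 1.35
- Cycles 6 and 7 both missed: 1.66

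**Delay rather than a full skip (t½ 18 d).** If the Cycle 7 dose comes 8 days late and is labelled Cycle 8, the gap is 22 days and the CL ratio is 1.21. If the Cycle 8 dose comes 7 days late and keeps its number, the ratio is still 1.17.

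**21-day cohort 1aD (t½ 18 d).** With Cycle 7 missed, the CL ratio is 1.33 and AI_AUC is 1.36 against 1.80.

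**Trough.** Before Cycle 8, after a 28-day gap, the trough is 0.560/0.977 = 0.57 of its on-schedule value at 18 days (0.30 to 0.66 over 8 to 25 days).

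**Effect of the pAUCe rule.** r exceeds 0.20 when t½ > 14 × ln2/ln5 = 6.0 days. Read literally, the rule therefore flags CL in the 14-day cohorts over the whole assumed range, with or without missed doses. It names AUC(INF) and CL. It does not name AI_AUC, AI_Cmin or Vss.

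**Cohort level.** No missed-dose rate is given. If 10% to 50% of patients missed Cycle 7 (t½ 18 d, individual AI_AUC ratio 1/1.327 = 0.754), the geometric mean AI_AUC would be multiplied by 0.754^0.1 = 0.97 to 0.754^0.5 = 0.87.

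**12-day minimum.** After a delay of d days, returning to the original calendar puts the next dose 14 − d days later, or 16 − d using the +2-day window. For d = 5 this is 9 (11), and for d = 6 it is 8 (10); all are below 12. For d = 3 or 4 the nominal dates fall short (11, 10), but the window can restore 13 or 12. In 1aD, 21 − 6 = 15, so there is no conflict. For exactly 7 days, 4.3.6 says which visit's procedures to perform, but neither rule for later visits (longer than 7, less than 7) applies.

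**The case against.** Several stronger readings are tempting, and the documents do not support them.

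- **That all accumulation indices and Ctrough are tied to Cycle 8.** They are not. AI_Cmax and AI_Ctrough may use any cycle, and Ctrough belongs to each interval. A trough after 28 days is a correct measurement for that interval. It is only not comparable with on-schedule troughs in a by-cycle or by-ADA-status table.
- **That CL is inflated in every patient with a held dose.** The bias fades quickly with distance from Cycle 8, and a hold after the Cycle 8 interval has none.
- **That renumbering is the whole cause.** A 7-day delay of Cycle 8 itself keeps the number and still gives 1.17.
- **That affected patients are a toxicity-selected group, or that a 2-week against 3-week comparison is contaminated.** Protocol 4.3.2 says drug-related laboratory abnormalities generally do not require a delay, 4.3.6 also allows personal reasons, and part of the delay criteria is redacted. Cohort 1aD is there to characterise PK, and no formal comparison is specified.

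The best counter-argument is the pAUCe rule: under the same model it already keeps 14-day-cohort CL out of the descriptive statistics. That stands, and it moves the weight of the point to AI_AUC, AI_Cmin and individually listed CL. The SAP also has discretionary routes: profile exclusion (7.7.4.3), the requirement for reliable derivation (7.2) and alternative PK modelling (7.7.4.1). These help, but none makes a missed dose a trigger.

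On the 12-day conflict, the minimum can fairly be read as an overriding floor, since it closes the same paragraph. The text does not say so.

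**Conclusion.** The point holds in a limited form. Following the plan as written, AI_AUC and AI_Cmin are biased down, and dose over AUC(TAU) overstates CL, in patients whose cabiralizumab dose was missed or delayed shortly before Cycle 8. With Cycle 7 missed, AI_AUC is about 20 to 25% low and CL is 1.26 to 1.36 times true. Misses at Cycle 2 or 4 matter little.

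The sizes rest on linear one-compartment kinetics and an assumed half-life. The SAP itself leaves dose-proportionality to be assessed. The cohort-level effect can only be bounded, because the documents give no missed-dose rate. All analyses are descriptive, so the primary endpoints and the sample size are unaffected.

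The conflict between the return-to-schedule rule and the 12-day minimum is a matter of arithmetic and depends on no PK model.

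**What to change.** **SAP 7.7.2 and 7.7.4.2.** Include Cycle 8 CL, Vss, AI_AUC and AI_Cmin in descriptive statistics only when the preceding cabiralizumab doses were given within the ±2-day visit window of the nominal interval (14 days, or 21 in 1aD). The last three intervals would be a workable choice. Flag and list the other values, and show the summary with and without them. With three intervals, the latest single miss that still passes is Cycle 4. At 18 days that leaves AI_AUC at 2.25 against 2.37, about 5% low.

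**Troughs of both drugs.** Include them in by-cycle and by-ADA-status summaries only when drawn within the window of the nominal interval since that drug's last dose, and list the rest.

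**Cost.** SAP wording and some programming on dosing dates already recorded on the CRF. Fewer values will enter the summaries, and those left may be a selected group; the with-and-without display makes that visible.

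**Protocol 4.3.6.** The return-to-schedule rule for delays under 7 days, the unstated scheduling after exactly 7 days, and the 12-day minimum (also in 4.3.1) must be reconciled. This review does not say which should govern.

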## **3.1.3 End-of-Treatment Follow-up Period**

All patients should return to the clinic 28 ( $\pm 7$ ) days and 100 ( $\pm 7$ ) days from their last dose of study drug to complete the End-of-Treatment Follow-up Period, irrespective of whether a patient is discontinued from the study drug at a planned visit or mid-cycle. AEs will be assessed until resolution, return to baseline, or are stabilized per treating Investigator's assessment. Adverse

event reporting will continue until 100 ( $\pm 7$ ) days after the last dose of study drug or until initiation of subsequent anti-cancer therapy.

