**3.4 Discontinuation of Patients following any Treatment with Study Drug**

Patients **must** discontinue study drugs for any of the following reasons:

- Withdrawal of informed consent (patient’s decision to withdraw for any reason)
- Any clinically significant AE, abnormal laboratory test results, or intercurrent illness which, in the opinion of the Investigator, indicates that continued participation in the study is not in the best interest of the patient
- Patients who are required to have prohibited concomitant medications

- Pregnancy
- Termination of the study by the Sponsor
- Loss of ability to freely provide consent through imprisonment or involuntary incarceration for treatment of a psychiatric or physical (e.g., infectious disease) illness
- Documented disease progression or clinical deterioration while receiving active study therapy
- Non-compliance by the patient

All patients who discontinue study treatment should comply with protocol specified follow-up procedures as outlined in Section 5.2.4. The only exception to this requirement is when a patient withdraws consent for all study procedures or loses the ability to consent freely (i.e., is imprisoned or involuntarily incarcerated for the treatment of a psychiatric or physical illness).

If a patient was discontinued, the reason for discontinuation must be entered on the appropriate CRF. The date and reason for cessation of cabiralizumab and/or nivolumab will be documented, and the Investigator must make every effort to perform the End-of-Treatment Visits. Adverse event reporting will continue until 100 ( $\pm 7$ ) days after the last dose of study drug or until initiation of subsequent anti-cancer therapy. Patients with ongoing SAEs will be followed until resolution or stabilization.

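### Protocol 4.3.6 takes patients off the study, not just off drug, after an AE-related dosing gap of more than 6 weeks, which conflicts with 4.3.5 and the general follow-up rules

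*Protocol*

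**What the plan says.** Protocol 4.3.6 sets the rule in one sentence. It opens "Omission of additional dosing longer than 6 weeks for AEs will necessitate the patient" and gives the consequence as "discontinuation from the study unless allowed by the Sponsor", the permission resting with the Medical Monitor or designee.

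Protocol 4.3.5 covers a delay of the same length. Its list opens "Treatment of cabiralizumab in monotherapy or cabiralizumab in combination with nivolumab should be discontinued in the following cases unless otherwise specified", so what stops is treatment. The relevant item reads "Any event that leads to delay in dosing lasting > 6 weeks from the previous dose requires discontinuation" and then gives exceptions. For AEs, "Dosing delays to manage drug-related adverse events are allowed", with the Medical Monitor consulted before dosing restarts. During such a delay, "Tumor assessments should continue as per-protocol even if dosing is delayed", and safety visits and laboratory tests also continue.

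Three general sections say what happens once drug is stopped:
- 3.1.3 requires visits at 28 (±7) and 100 (±7) days after the last dose for all patients, "irrespective of whether a patient is discontinued from the study drug at a planned visit or mid-cycle".
- 3.4 says "All patients who discontinue study treatment should comply with protocol specified follow-up procedures as outlined in Section 5.2.4". It excepts only withdrawal of consent for all procedures and loss of the ability to consent freely.
- 5.2.4 continues follow-up until death, loss to follow-up, withdrawal of consent or termination of the study.

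The SAP keeps the two kinds of discontinuation apart. Section 7.3.1 tabulates treatment discontinuation and study discontinuation separately, each with reasons. Section 7.5 counts tumor assessments towards best overall response only up to the earliest of several events, one of which is discontinuing from the study.

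**The concern.** Two adjoining sections give different consequences for a dosing gap of the same length. One stops the drug; the other, read as written, ends participation. The patients concerned are selected for toxicity, so their later follow-up matters for safety and efficacy alike.

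The losses at stake are the 100-day visit, tumor scans after the gap, and survival contact. In Phase 1b the primary efficacy endpoint is confirmed ORR. A first CR or PR whose confirming scan is never done, or is done after the recorded study discontinuation, would not count as a response. PFS and DOR would be censored at the last evaluable scan, and OS at the last date known alive.

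The sections also differ, narrowly, on restarting. For drug-related AEs, 4.3.5 asks for consultation with the Medical Monitor, whereas 4.3.6 asks for permission.

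**Working it through.** The plan states no figure on this point. The check compares the sections and then works out the timing.

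**1. The sections side by side**

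| Protocol section | Trigger | What stops | What continues |
|---|---|---|---|
| 4.3.6 | AE-related omission over 6 weeks | The study, unless the Medical Monitor or designee allows otherwise | Not stated |
| 4.3.5 | Delay over 6 weeks from the previous dose | Treatment, with exceptions | Scans, safety visits and laboratory tests during the delay |
| 3.1.3 | Last dose, however treatment ended | – | 28- and 100-day visits |
| 3.4 | Any stop of treatment | Drug | Follow-up under 5.2.4; consent-related exceptions only |
| 5.2.4 | End of the End-of-Treatment period | – | Survival contact every 12 (±2) weeks; scans for patients who left treatment with CR, PR or SD |

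Only 4.3.5 addresses the long delay itself. The last three rows are general rules. They conflict with 4.3.6 because a dosing delay is not among their exceptions or end points.

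**2. The End-of-Treatment visits against the 6-week limit**

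Count days from the last dose. The limit is 6 × 7 = 42 days.
- 28-day visit window: 28 − 7 = 21 to 28 + 7 = 35. It closes 42 − 35 = 7 days before the limit.
- 100-day visit window: 100 − 7 = 93 to 100 + 7 = 107. It falls 93 − 42 = 51 to 107 − 42 = 65 days after the limit.
- If the 6 weeks run instead from the first missed two-weekly dose, the limit is 14 + 42 = 56 days. The visit then falls 93 − 56 = 37 to 107 − 56 = 51 days after it.

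On either count the 100-day visit lies beyond the limit.

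**3. Confirmation of response**

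SAP 7.5 requires confirmation at least 4 weeks (28 days) after the first CR or PR. Off treatment, the next required scan is one at an End-of-Treatment visit, unless waived because a scan was done within the previous 8 weeks (56 days; Protocol 5.2.3.8), or a 12-weekly follow-up scan (3.5, 5.2.4).

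Two illustrations follow. Both assume first dose on day 0, two-weekly dosing on schedule, a first PR on day 56, and the limit counted from the last dose.

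*Last dose at Cycle 3, day 28.*
- Limit: 28 + 42 = day 70.
- Earliest confirmation: 56 + 28 = day 84, after the limit.
- The 28-day post-dose scan falls on 28 + 28 = day 56, the response scan itself, so it cannot confirm.
- The 100-day visit falls on days 28 + 93 = 121 to 28 + 107 = 135. That is 65 to 79 days after the day-56 scan, so the 8-week waiver does not apply and a scan is due.
- Removal from the study after day 70 loses that scan, or places it after the SAP cut.

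*Last dose at Cycle 5, day 56.*
- Limit: 56 + 42 = day 98.
- Protocol 5.2.3.7 schedules a scan 28 (±7) days after the last dose, nominally 56 + 28 = day 84. That is the earliest confirmation date and lies before the limit, so the response could be confirmed in time.
- That scan may be waived, because the day-56 scan is only 28 days old.

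Whether a response is lost therefore depends on individual dates.

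**4. What the SAP rules add**

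If no scan is done after removal, the 7.5 cut changes nothing further; the data are simply missing. The cut matters when a scan is done but study discontinuation has already been recorded. In SAP Table 3, the row for study discontinuation and the row for no death or progression both censor PFS at the last evaluable assessment, so the former adds no censoring of its own.

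**The case against.** The strongest reply is that this is loose wording. Section 4.3.6 is about dosing and nowhere says that visits, scans or survival contact end. Section 3.4 also speaks of patients being discontinued when it means discontinued from drug, and then sends them to follow-up. Sections 3.1.3 and 5.2.4 cover all patients. Read as a whole, the protocol probably intends what the fix would say.

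Much of this stands. Stopping drug is the likelier intent, and harm needs a chain of conditions: an AE-related gap over 6 weeks, no allowance from the Medical Monitor, a site taking the phrase literally, and, for ORR, a response not yet confirmed. But the phrase is operative text. The same paragraph of 4.3.6 speaks separately of resuming study drug and of participating in the study, so a literal reading has support there. The SAP also gives the two kinds of discontinuation different consequences.

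Three stronger readings are tempting and are not supported:
- A reader might infer that the lost scan is the week-16 one, and count the dosing cycles at risk from that. Protocol 5.2.3.7 ties the 8-weekly scans to patients who remain on treatment, so week 16 is not necessarily the next scan for a patient who has stopped.
- A reader might infer that AE and SAE reporting would lawfully end at removal. Sections 3.4, 6.1 and 6.2.1 require it until 100 (±7) days after the last dose or the start of subsequent anti-cancer therapy. Its loss is only a risk from mixed instructions.
- A reader might infer that SAP Table 3 imposes extra censoring on these patients. It does not, as shown above.

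**Conclusion.** The contradiction is real and should be corrected. Section 4.3.6, read literally, ends study participation for an event that 4.3.5 treats as a reason to stop treatment and that 3.1.3, 3.4 and 5.2.4 do not exempt from follow-up.

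What can be sized is the timing: the 100-day visit comes 51 to 65 days after a limit counted from the last dose, or 37 to 51 days after one counted from a missed two-weekly dose. Later off-treatment scans and survival contact are also exposed, and an unconfirmed CR or PR could drop out of confirmed ORR.

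This rests on a site following 4.3.6 as written and on no allowance being given. The documents give no rate of such gaps or of allowances, so neither the number of patients affected nor the direction of any bias can be determined. It is a wording conflict with a possible effect on the primary endpoint, not a demonstrated loss of data.

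**What to change.** In Protocol 4.3.6, replace the phrase on leaving the study with *discontinuation of study drug, with follow-up per 3.1.3, 3.4 and 5.2.4*. In the same sentence, refer to the 4.3.5 exceptions for drug-related AEs, so that one rule governs restarting.

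The cost is one phrase and one cross-reference. No visit or scan is added beyond those the protocol already requires. SAP Table 3 needs no change on this account: its event row already takes the earlier of death or first documented progression, and relabelling the study-discontinuation row would alter no result.
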